3.1 Primary Analysis: Motor or Stereo Deterioration

Participants who meet either of the following at any visit will be considered to have met deterioration criteria.

- Motor deterioration: Control of the exodeviation measures 5 (constant exotropia) on all three assessments at distance and near. The exodeviation does not need to be constant throughout the entire exam provided that it is constant during all three assessments of control. (The study requires that a participant cannot be enrolled if the control of the exodeviation at near measures 5 on all three assessments at baseline; hence all participants in the study are eligible for motor deterioration.)
- Stereoacuity deterioration: Drop in near stereoacuity of at least 2 octaves (at least 0.6 log arcsec) from enrollment stereoacuity, or to nil, confirmed by a retest. (Participants with nil stereoacuity at enrollment will not be able to deteriorate with respect to a drop in near stereoacuity but are included in the analysis as they may have motor deterioration.)

299 Hazard of deterioration from a proportional hazards model will be compared by treatment
300 group using the hazard ratio, and cumulative proportions deteriorating in each treatment
301 group at 12 and 18 months will be reported. The cumulative proportion estimates from
302 the proportional hazard model will be compared between treatment groups using a Z-test
303 for proportions if at least one of the proportions is between 0.05 and 0.95. If both
304 proportions are not between these two numbers, they will not be compared statistically.
305 The proportional hazards model will adjust for baseline level of the components of the
306 outcome, i.e. distance control, near control, and near stereoacuity. The population mean
307 of the covariates in the proportional hazards model will be used for cumulative
308 probability estimation. We will only adjust for these baseline-level components of the
309 outcome because deterioration rates were low in IXT2,¹ making adjustment for more than
310 a few covariates potentially problematic. The observed data will be used in these
311 analyses.

312
313 Any observation with a missing value for any of the baseline factors will be excluded
314 from the analysis. However, the number of missing values is expected to be low given
315 that the testing of these baseline factors is required at enrollment by protocol. If either
316 motor or stereo outcome data are missing at a follow-up visit and these data are available
317 at a later visit, the deterioration status will be carried forward from the visit previous to
318 the missing visit. The participants who are lost to follow up without meeting deterioration
319 criteria will be considered censored as of the last completed follow-up visit.

320
321 The participants who start non-study treatment (i.e., treatment other than overminus or
322 non-overminus) for IXT will be censored 0.1 month after the visit when the non-study
323 treatment was prescribed. Participants who are treatment crossovers (non-overminus
324 group participants who are prescribed overminus; overminus group participants who have
325 overminus spectacles formally discontinued against protocol) will have observed
326 deterioration status data included in analysis, i.e., will not be censored on the basis of
327 starting a non-randomized treatment (i.e., any treatment other than the one assigned by
328 the study at randomization). The proportional hazards model time variable will be
329 discrete with times corresponding to the follow-up time of study visits.

330
331 The proportional hazards assumption will be checked by testing for a time by treatment
332 interaction in the model, as well as by visual inspection of Kaplan-Meier time-to-event
333 curves. In the event the proportional hazards assumption is not met, an alternative
334 analysis such as a weighted, stratified comparison of Kaplan-Meier estimates will be
335 considered.

336
337
338

339 **3.2 Secondary Analysis: Cause-Specific Deterioration**

340 If the overall deterioration treatment group comparison (Section 3.1) is performed and is
341 significant, then the cumulative incidence of cause-specific deterioration (stereo ONLY
342 and motor ONLY) by 12-months and 18-months will be estimated and compared between
343 the treatment groups using the cumulative incidence function to account for the
344 competing risks of starting treatment due to deterioration from a cause other than the

345 cause of interest, or starting treatment against protocol. To control for multiplicity, alpha
346 will be split between the two time points (12 and 18 months), and a gatekeeping strategy
347 will be used within each time point, i.e., the 18-month difference will be tested only if the
348 12-month difference is statistically significant. These analyses are considered post-hoc, as
349 they were not included in version 1.0 of the protocol or SAP. Because using stereoacuity
350 as the (sole) outcome for IXT has ample precedent in the literature, an additional analysis
351 will be conducted using a post-hoc alternative definition of deterioration which classifies
352 the participant's condition as deteriorated only if the participant met stereo deterioration
353 criteria. *Unlike for the analysis of overall deterioration, participants with nil stereo at*
354 *baseline will be excluded from this analysis.* The analysis will be adjusted for baseline
355 near stereoacuity.

356
357

358 **4. Objective III: Other Clinical Outcomes, Exploratory Analyses, and Safety**

359 The analyses specified below will use the observed data and only the visits that occurred
360 within the analysis window will be included. For all outcomes, the data will be tabulated
361 and means and standard deviations, or proportions, will be calculated for each of the
362 treatment groups. The type I error rate for analyses of the secondary outcomes specified
363 in the sections below will be controlled using false discovery rate (FDR) to account for
364 the multiple outcomes. The outcomes will be divided into 2 groups for this purpose, with
365 FDR controlled at the 5% probability level within each group. The first group is
366 comprised of the clinical measures (no spontaneous tropia, near control, angle magnitude,
367 stereoacuity, axial length and other biometric measures, and refractive error) and the
368 second is comprised of the symptom and quality of life measures.

369

370 **4.1 Other Clinical Outcomes at 12 and 18 Months**

371

372 For the 18-month visit, all analyses will be repeated, limited to participants who were
373 prescribed weaning (i.e., prior to weaning being discontinued per Protocol Amendment
374 II). This will be done because if retention of an on-treatment effect is stronger in
375 participants who have full weaning vs. less than full weaning, the 18-month treatment
376 effect could be diluted in the full cohort analysis vs. the limited cohort.

377

378 **4.1.1 No Spontaneous Tropia**

379 The proportion of participants with no spontaneous tropia will be compared between the
380 two treatment groups using a two-sided Barnard's test (with alpha of 0.05) at 12 months
381 and 18 months. The difference in proportions, a two-sided 95% confidence interval, and
382 p-value on the difference in proportions will be calculated.

383

384 No spontaneous tropia during control testing at the 12-month (and 18-month) exams
385 means the following must have been true during the examination:

- 386 • Score of ≤ 2 (2 or better) on all three assessments of control at distance and at near

387

388 While the definition originally specified "No spontaneous tropia at any time during the
389 exam at distance or near," the way the question was posed on the CRF did not allow us to
390 differentiate between spontaneous and non-spontaneous tropia for the period of time

391 outside of control testing for patients who were classified as having intermittent tropia.
392 Therefore, we changed the definition to only be based on presence of spontaneous tropia
393 during control test scores, as detailed above.

394

395 The proportion of participants with no spontaneous tropia during control testing at 12
396 months (and 18-months) will also be tabulated for each treatment group within the
397 subgroups specified below, if the overall effect was significant. The estimate or treatment
398 difference and 95% confidence interval will be reported.

- 399 • Spontaneous tropia (as defined above) at baseline (Yes vs. No)
- 400 • Severity of baseline distance control (2 to <3, 3 to <4, 4 to 5)

401

402 **4.1.2 Change in Distance Control**

403 Distance control will be reported as the distributions of baseline level of control, 12-
404 month (primary outcome), and 18-month control, and *change in control* from baseline to
405 12 months, and 18-months, including the proportion with ≥ 1 -point change in control and
406 proportion with ≥ 2 -point change.

407

408 The proportion of participants with ≥ 1 -point improvement in distance control between
409 baseline and 12 months (18 months) will be compared between the treatment groups
410 using a two-sided Barnard's test with alpha of 0.05, with calculation of a two-sided 95%
411 confidence interval and p value on the difference in proportions. The proportion of
412 participants with ≥ 2 -point improvement in distance control between baseline and 12
413 months (18 months) will be compared between the treatment groups similarly.

414

415 **4.1.3 Additional Sensitivity Analyses**

416 The treatment group comparisons of distance control score at the 12-month and 18-month
417 visits will be repeated excluding the 28 participants whose treatment assignment was
418 based on the incorrect row from the randomization schedule (Section 2.1.1), regardless of
419 whether the incorrectly-assigned value matched the assignment that would have been
420 chosen if the correct record from the randomization schedule was used. The imputed
421 dataset specified in Section 2.1.9 will be used. The results will be compared to the
422 original analyses to assess if bias was introduced by including these 28 participants who
423 were included in in the primary analyses despite being incorrectly randomized.

424

425 **4.1.4 Near Control**

426 At the 12 and 18-month time points, near control will be evaluated similarly to the
427 distance control primary analysis (Section 2).

428

429 **4.1.5 Angle Magnitude by PACT**

430 At the 12- and 18-month time points, a two-sided treatment group comparison of
431 magnitude of the deviation by Prism Alternate Cover Test (PACT) will be performed
432 using an ANCOVA model which adjusts for baseline PACT. The treatment group
433 difference, 95% confidence interval and p value will be calculated. The analysis will be
434 completed separately for distance PACT and at near PACT.

435

436 **4.1.6 Stereoacuity**

437 At the 12 and 18-month time points, a two-sided treatment group comparison of near
438 stereoacuity (measured with the Preschool Randot Test) will be performed using an
439 ANCOVA model which adjusts for baseline stereoacuity. The treatment group difference,
440 95% confidence interval, and p value will be calculated.

441

442 **4.1.7 Axial Length Measurement**

443 At the 18-month time point, mean axial length measurement will be compared between
444 treatment groups using an ANOVA model. The treatment group difference and a 95%
445 confidence interval will be calculated. Adjustment for baseline is not possible given that
446 these measurements were added late in the study (with Protocol Amendment II) and
447 therefore not collected at baseline.

448

449 **4.1.8 Additional Ocular Biometric Parameters**

450 At the 18-month time point, mean flat corneal radius, anterior chamber depth, and lens
451 thickness will each be compared (if available) between treatment groups using an
452 ANOVA model. The treatment group difference and a 95% confidence interval will be
453 calculated. Adjustment for baseline is not possible given that these measurements were
454 added late in the study (with Protocol Amendment II) and therefore not collected at
455 baseline.

456

457 **4.1.9 Refractive Error**

458 At the 12- and 18-month time points, a two-sided treatment group comparison of
459 spherical equivalent refractive error will be performed using an ANCOVA model which
460 adjusts for baseline refractive error and baseline age. The latter was added as a post-hoc
461 adjustment factor, as age is expected to be associated with refractive error at the 12-
462 month (and 18-month) time points. The treatment group difference, 95% confidence
463 interval, and p-value will be calculated. This analysis will be done combining refractive
464 error obtained by subjective refraction or retinoscopy and separately from refractive error
465 obtained by autorefraction.

466

467 **4.1.10 Quality of Life**

468 At both the 12-month and 18-month time points, a two-sided treatment group comparison
469 of the child, and each of the three parent scales in the IXTQ HRQOL (Quality of Life)
470 will be performed each using the Wilcoxon Rank Sum Test as it is expected that scores
471 will not be normally distributed and will have a substantial ceiling effect. The treatment
472 group difference, 95% confidence interval, and p value will be calculated for both the
473 Rasch-scored data¹ and for 0 to 100-scaled data. The reported p-value will be derived
474 from the analysis of Rasch-scaled data, while to aid in interpretation, the 0 to 100-scaled
475 data will be used when reporting the median values for each treatment group.

476

¹ Leske DA, Holmes JM, Melia M, on behalf of Pediatric Eye Disease Investigator Group. Evaluation of the Intermittent Exotropia Questionnaire using Rasch analysis. JAMA Ophthalmol 2015;133:461-5.

477 A potential secondary manuscript, to be detailed in a separate SAP, will describe quality
478 of life, IXT symptoms, and spectacle wear issues, the relationships among these, and
479 relationships between these and clinical measures.

480

481 **4.1.11 IXT Symptom Survey**

482 A 7-item survey of IXT-related symptoms will be completed by the child at the
483 enrollment, 6-month, 12-month, and 18-month outcome exams. For each IXT-specific
484 symptom, the child is asked how often it occurs, using the response choices of “never”
485 “sometimes”, and “all the time.” The distribution for each individual item will be
486 tabulated for each treatment group for each outcome time point.

487

488 A 7-item survey consisting of IXT-related symptoms and problems with spectacle wear
489 will be completed by parents of participants at the enrollment, 6-month, 12-month, and
490 18-month exams. The parent is asked how often symptoms or problems occur, using the
491 response choices of “never,” “almost never,” “sometimes”, “often”, “almost always.” The
492 distribution for each individual item will be tabulated for each treatment group for each
493 outcome time point.

494

495 **4.1.12 Compliance with Spectacle Wear**

496 Compliance with spectacle wear will be assessed at the 6-month, 12-month, 15-month,
497 and 18-month exams. Parents will provide an estimate of the proportion of the time their
498 children wore their spectacles. Proportion of time worn will be described as excellent
499 (76% to 100%), good (51% to 75%), fair (26% to 50%), or poor ($\leq 25\%$). The
500 distribution of compliance will be tabulated for each treatment group for each time point.

501

502 **4.2 Exploratory Analyses**

503 The following exploratory analyses will use observed or imputed data (see LOCF,
504 below), as follows:

- 505 • All participants who complete one or more distance control assessments at a specific
506 visit within the corresponding analysis window, including treatment crossovers, will
507 have their observed data analyzed, except for participants who are prescribed non-
508 study treatment (i.e., IXT treatment other than overminus or non-overminus refractive
509 correction), who will have the distance control from the (first) visit when non-study
510 treatment was prescribed carried forward.
- 511 • Participants who miss the study visit entirely or who do not complete any control
512 assessments at the visit will be excluded from the analysis for that visit.
- 513 • Participants who had the visit completed outside of the analysis window will be
514 excluded from the analysis for the visit.

515

516 **4.2.1 Mean Distance Control in Baseline Subgroups**

517 The treatment group comparisons of 12-month distance control will be assessed in
518 subgroups based on baseline factors. Subgroup comparisons for 18-month distance
519 control will be explored only if there is an overall treatment group difference in distance
520 control at 18 months. All planned subgroup analyses will repeat the primary analysis
521 (Section 2, excluding the sensitivity analysis). The specific subgroups of interest are:

- 522 • Baseline distance control score by severity (2 to <3, 3 to <4, 4 to <5 points)

- 523 • Baseline age group (3 to <7 years vs. 7 to <11 years)
- 524 • Spherical equivalent refractive error level (-6.00 to -0.50D vs. -0.375 to +1.00D)
- 525 • Accommodative convergence/accommodation (AC/A) ratio (<2.5, 2.5 to 6.0, >6)

526

527 Exploratory analyses performed on the IXT3 pilot study data suggested that overminus
 528 spectacles might be effective for participants with very poor baseline distance control (4-
 529 <5 points), a finding that was somewhat unexpected. We would like to further explore
 530 whether treatment effect varies by baseline control. Because children 7 to < 11 years of
 531 age likely have greater accommodative demands (e.g., schoolwork) than children 3 to < 7
 532 years of age, and because the visual systems of the two groups are at different stages
 533 developmentally, it is possible that their response to overminus lenses might be different.
 534 Since participants with hyperopia and participants with myopia may use their
 535 accommodative system differently, the response to overminus lenses may be different.
 536 We might expect that participants with high AC/A ratios would respond to overminus
 537 spectacles better than participants with lower AC/A ratios given that one of the
 538 mechanisms of action of overminus is to stimulate accommodative convergence, thereby
 539 reducing the angle of exodeviation and allowing fusion. The IXT3 pilot study showed a
 540 similar treatment effect of overminus in participants with AC/A <2.5 and >=2.5 but had
 541 very few participants with very high AC/A (i.e., larger than 6).

542

543 Subgroup analyses will also be conducted for gender and race/ethnicity in accordance
 544 with NIH guidelines; however, no effect modification is expected for these factors.

545

546 A summary of the subgroups and expected directions of effect modification is shown in
 547 Table 1.

548

549

550

551

552

553

Table 1 – Subgroup Analyses

Factor	Grouping	Expected Direction	Rationale
Baseline age (years)	3 to <7 7 to <11	Better treatment effect expected in 3 to <7 group	Younger children typically have a greater accommodative amplitude and engage in less sustained near activities than older children and may more completely accommodate, thereby inducing accommodative convergence which is

			a postulated mechanism for overminus
Baseline distance control	2 to <3 3 to <4 4 to <5	Larger treatment effect expected in participants with worse control (4 to <5)	Observed in IXT3. Possibly, participants with worse control have more room to improve / less ceiling effect. They also are expected to have more regression to the mean.
Refractive error (D)	-6.00 to -0.50 (myopic) -0.375 to +1.00 (not myopic)	Better treatment effect expected in non-myopes	Myopes are likely to get more myopic during the study, which would lessen the true effect of overminus glasses.
AC/A ratio	<2.5 2.5 to 6.0 >6	Better treatment effect expected in participants with higher AC/A ratios (>2.5)	Higher AC/A is associated with greater convergence per unit of accommodation, and accommodative convergence is a postulated mechanism of overminus effect

554

555

556 The descriptive data tabulations and figures of the subgroups will be based on the
557 observed data. The subgroup analysis will not be done if the sample size in a subgroup is
558 less than 20 participants for any subgroup level within treatment group.

559

560 A Forrest plot will be generated, which will display estimates of difference between
561 treatment groups and 95% confidence intervals for every subgroup. P-values will not be
562 reported.

563

564 In addition to the baseline factors specified above, the treatment group comparisons of
565 12-month and 18-month (if there is an overall effect) distance control will also be
566 assessed in subgroups based on the use of ADHD medications at any time between
567 baseline and the 12-month visit (yes/no). ADHD medication may reduce accommodation
568 and could make overminus treatment less effective. Note: As the criteria used to
569 categorize use of ADHD medications is based on post-randomization factors (i.e., use of
570 medication during the follow-up), this could potentially introduce bias into the treatment

571 group comparison. The treatment effect in these subgroups will be interpreted with
572 particular caution.

573

574 **4.2.2 Mean Distance Control at 18 Months According to Prescribed Weaning** 575 **Status**

576 Of the 355 expected 18-month visits (as of 11/5/19), approximately 283 participants
577 (80%) will have completed a full 3-months of prescribed weaning before discontinuing
578 overminus (or non-overminus); approximately 35 to 54 (20% to 25%) participants will
579 have completed partial weaning, and approximately 18 to 37 participants (5% to 10%) are
580 expected to have no weaning at all per Protocol Amendment II. The summary statistics
581 for distribution of 18-month distance control and change from baseline in distance control
582 will be tabulated according to treatment group and whether full, partial, or no prescribed
583 weaning.

584

585 **4.2.3 Participants with Baseline Control of 3 to 5 Points (Spontaneous Tropia)**

586 Participants with baseline distance control of 3 to 5 points may have a better likelihood of
587 improving ≥ 2 points. The mean distance control of these participants is indicative of the
588 presence of spontaneous tropia on at least one of the 3 control measures, while
589 participants with mean distance control scores of 2 to <3 points had a phoria on one or
590 more of the control measures.

591

592 If there is no evidence of a treatment effect in the subgroup of participants with mean
593 distance control scores at baseline of 2 to <3 points (from Section 4.2.1), the distance
594 control primary analysis (Section 2, excluding sensitivity analysis) and secondary
595 analysis (Section 2.3) will be repeated in exploratory analyses limited to the cohort of
596 participants with baseline distance control of 3 to 5 points. This will be done at both the
597 12-month and 18-month time points.

598

599 [Note: this is included in the SAP only because it appeared in the Protocol. It is
600 recognized that in the event this analysis is carried out as specified, strict control over the
601 type I error rate will have been lost.]

602

603

604 **4.3 Safety Analyses**

605

606 **4.3.1 Refractive Error at 12 and 18 Months**

607 The proportion of participants with >1 D increase in myopia or in hyperopia from
608 baseline to 12 months and from baseline to 18 months will be tabulated separately by
609 direction of change (myopic or hyperopic), and treatment group, for refractive error as
610 measured by subjective refraction or retinoscopy and also for refractive error as measured
611 by autorefraction. The risk ratio for myopia progression of >1 D will be calculated for the

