5.3.1 Additional Secondary Outcomes

Analysis of near control, angle magnitude, stereoacuity, and treatment compliance will be performed as described below.

5.3.1.1 **Deterioration**

At both the 12-month and 18-month time points, the cumulative proportion of subjects who meet either of the deterioration criteria (*section 3.7*) by the time point will be estimated for each treatment group using the proportional hazards model to enable adjustment for potential residual confounding. The adjusted cumulative probability estimate will then be compared between treatment groups using the Z-test. The cumulative proportion of patients who meet stereoacuity deterioration criteria by the time point and the cumulative proportion of patients who have constant exotropia by the time point will also be estimated and compared between treatment groups using similar methods. Analytic methods which account for possible informative censoring will be explored for handling subjects who start non-randomized treatment for IXT. Such methods will also be explored for the stereoacuity deterioration and motor deterioration outcomes.

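### The Z-test for proportions in SAP 3.1 does not fit cumulative deterioration proportions predicted from one proportional hazards model; on the natural reading it makes the 12-month comparison conservative

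*SAP*

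**What the plan says.** SAP 3.1, the primary analysis of Objective II, fits a proportional hazards model for motor or stereoacuity deterioration. The model adjusts for baseline distance control, near control and near stereoacuity. Its time variable is "discrete with times corresponding to the follow-up time of study visits". Cumulative proportions at 12 and 18 months are predicted at the population mean of the covariates. The estimates from "the proportional hazard model will be compared between treatment groups using a Z-test" "for proportions if at least one of the proportions is between 0.05 and 0.95"; otherwise there is no statistical comparison.

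The same section also states: "Hazard of deterioration from a proportional hazards model will be compared by treatment" group, by the hazard ratio.

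Protocol 5.3.1.1 has the same step without the words on proportions: "The adjusted cumulative probability estimate will then be compared between treatment groups using the Z-test".

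Neither document gives the standard error, says whether the 12-month estimate uses events after 12 months, or gives an expected rate beyond the SAP's remark that rates were low in IXT2. SAP 3.2 runs the cause-specific analyses only if the 3.1 comparison is performed and significant. It does not say whether that means the hazard ratio, the 12-month Z-test or the 18-month Z-test.

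**The concern.** A two-sample Z-test for proportions assumes two independent binomial proportions, each with variance p(1−p)/n. The quantities in SAP 3.1 differ in three ways:

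- Both arms' predictions use the same baseline hazard and the same treatment coefficient, so they are correlated.
- If the model is fitted to all follow-up, events after 12 months sharpen the coefficient and hence the 12-month difference. The binomial formula ignores this.
- Prediction at the covariate means gives the risk of an average child, which is lower than the average risk, and the binomial formula does not reflect that either.

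At 12 months all three make the binomial standard error too large. The Z-test p-value in SAP 3.1 is then unreliable. If that test decides whether SAP 3.2 is run, so is the decision to open the cause-specific analyses.

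**Working it through.** **1. Sample size.** Protocol 5.7.1 and 5.7.2 use SD 1.8, difference 0.65, two-sided alpha 0.05 and 90% power. The normal formula gives 2(1.96+1.282)²(1.8²)/(0.65²) ≈ 161.2, so 162 per group; the t-test gives 163 (326 in total), as stated. Then 163/0.90 = 181.1, so 182 (364 in total), and 163/0.85 = 191.8, so 192 (384 in total). These match. They concern distance control; the documents give no power figure for deterioration. Only the 192 per group is carried forward.

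**2. Size of the mismatch.** Take no treatment effect, small risks and no covariates. Let p12 be the 12-month risk and q18 the proportion with an event over all follow-up.
- The predicted difference is about p12 × β̂, with Var(β̂) ≈ 4/(384·q18). Its variance is therefore about 4·p12²/(384·q18).
- The binomial variance is 2·p12(1−p12)/192 ≈ 4·p12/384.
- The ratio is p12/q18, so Z has SD of about √(p12/q18) instead of 1.

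If two thirds of the hazard falls by 12 months, the SD is √0.667 = 0.816 and type I error is 2Φ(−1.96/0.816) = 1.6%. If half does, the SD is 0.707 and the error 0.56%. A comparison with 80% power under the right standard error drops to 65.5% or 51.2%.

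**3. Simulation with covariates and loss.** From the documents: 192 per group, visits at 6, 12, 15 and 18 months, loss of 10% by 12 months and 5% more by 18. Assumed, because the documents give no values: 12-month rate in the non-overminus group 5%, 10% or 20%; share of the 18-month hazard falling by 12 months 2/3 or 1/2; SD of the covariate linear predictor 0, 0.5 or 1.0; hazard ratio 1 or 0.5; two-sided alpha 0.05. One model was fitted to all follow-up. The tested statistic was Z = (p1−p0)/√(p̄(1−p̄)·2/192). There were 2,500 trials per scenario (simulation error about 0.4 points on a 5% rate and 1 point on power). The 0.05–0.95 rule was not applied to the rejection rates.

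12-month results at a 10% rate:

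| Hazard by 12 mo | Covariate SD | Type I, binomial | Type I, delta | Power (HR 0.5), binomial | Power, delta | Power retained |
|---|---|---|---|---|---|---|
| 2/3 | 0 | 2.3% | 4.6% | 40.5% | 54.5% | 0.74 |
| 2/3 | 0.5 | 1.6% | 4.8% | 35.2% | 52.7% | 0.67 |
| 2/3 | 1.0 | 0.6% | 3.8% | 19.4% | 48.4% | 0.40 |
| 1/2 | 0 | 0.8% | 4.6% | 39.1% | 63.8% | 0.61 |
| 1/2 | 0.5 | 0.4% | 4.6% | 35.2% | 64.9% | 0.54 |
| 1/2 | 1.0 | 0.0% | 4.0% | 16.5% | 61.0% | 0.27 |

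- Over all 18 null scenarios, type I error is 0.0%–2.6% with the binomial standard error, 2.2%–5.6% with the delta method, and 4.0%–5.5% for the Wald test of the hazard ratio.
- Power retained is 0.17–0.67 at a 5% rate, 0.27–0.74 at 10% and 0.63–0.87 at 20%.
- At 18 months the binomial test has error 4.3%–6.5% without strong covariates and 1.5%–2.8% with them.

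**4. Simpler setting.** With no covariates, no loss and hazard ratio 0.4, a hazard of 3% per visit gives power 34% by the Z-test and 66% by the Wald test (34/66 = 0.52). With early events (3, 3, 1, 1% per visit) it is 37% against 47% (0.79).

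**5. Other readings of the SAP.**
- Model fitted to 12 months only: 12-month type I error is 5.2%–5.6% with no covariate effect, 3.7%–4.7% with a moderate effect and 1.0%–1.8% with a strong one.
- Model standard errors used, but the arms treated as independent: 0.3%–3.6%.

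**The case against.** The strongest reply is that the defect is read into the text. No standard error is written, and an estimated difference divided by its model-based standard error is also a Z-test. The protocol says only the Z-test. Nor is the data span written, and a model cut at 12 months largely removes the problem unless covariates are strong. This stands in part. But the SAP names a test for proportions and attaches a 0.05–0.95 rule of the kind that suits a binomial normal approximation. It describes one model and no truncation. Using the model's standard errors without their covariance is still wrong.

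Four further points stand:
- The hazard-ratio comparison in the same section is valid and unaffected.
- The power gained over the 12-month Z-test comes from events after 12 months and assumes a constant hazard ratio while overminus is weaned or stopped. The SAP itself plans to check proportionality, with a Kaplan-Meier alternative. In the 3%-per-visit setting cut at 12 months, the Z-test has 38% power and the Wald test 33%.
- At low rates the 0.05–0.95 rule often means that no Z-test is run: at a 5% rate with no effect, only 7%–59% of simulated trials qualified at 12 months.
- Deterioration is an additional secondary outcome in the protocol, and the SAP labels the 3.2 analyses post hoc.

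**Conclusion.** The test named in SAP 3.1 does not fit the estimates it is applied to. With one model fitted to all follow-up, the 12-month comparison has type I error of about 0%–3% instead of 5%, and less power. Roughly half the power is kept in some low-rate scenarios with constant hazard per visit, and about 75%–85% when most events are early. The full range over the assumed scenarios is 17%–87%. All these sizes rest on assumed event rates, timing, covariate strength and hazard ratios.

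A reader might infer more than the documents support:
- **That the 12-month test loses half its power.** No event rate or effect is given, so no single figure can be stated.
- **That Objective II has no valid test.** The hazard ratio is one, and the SAP does not say that the Z-test takes precedence over it.
- **That false positives are inflated.** An illustrative loss of 20% before each visit gave 11%–12% error at 18 months, but the planned loss is 10% plus 5%, where the 18-month error stayed at or below 6.5%.

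The primary 12-month distance-control analysis is not affected.

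**What to change.** In SAP 3.1, replace the Z-test for proportions with the 12- and 18-month risk differences from the fitted model. Give each a confidence interval from a delta-method or bootstrap standard error that includes the covariance between arms. With few events and strong covariates the delta method was itself somewhat conservative (2.2% at worst), so the bootstrap is a reasonable choice there.

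State whether the 12-month estimate comes from all follow-up or from data to 12 months only. Name the comparison that opens SAP 3.2, for example the Wald or likelihood-ratio test of the treatment term already reported as the hazard ratio. The SAP should also say that this replaces the Z-test in Protocol 5.3.1.1.

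The cost is a few sentences of SAP text. Standard software gives these standard errors, and no data collection changes.
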